10.1 Demographics

Demographic and baseline characteristics including sex, age, race, ethnicity, education, and any other factors used in the minimization randomization procedure will be tabulated for each group. The distribution of subjects, including number and percentage of subjects, will be shown for the categorical variables. The univariate summary statistics n , mean (SD), median, minimum, and maximum will be calculated for the continuous variables.

10.2 Medical History

The number and percentage of subjects with a medical history either by body system and preferred term or by relevant disease specific history will be summarized by treatment arm.

10.3 Family History of Alzheimer's Disease

A family history of dementia as indicated by symptoms, history or diagnosis will be summarized by descriptive statistics. Mutation gene types (*PSENI*, *PSEN2*, and *APP*), number and percentage

of blood grandparents and parents, siblings, and children in a family with dementia will be tabulated by treatment arm.

10.4 Columbia – Suicide Severity Rating Scale (C-SSRS)

The C-SSRS score at screening and baseline will be summarized using descriptive statistics by severity rating scale for each category of Suicidal Ideation, Intensity of Ideation, Suicidal Behavior and Actual Attempts.

11 TREATMENT COMPLIANCE, CONCOMITANT MEDICATIONS, AND SUBSTANCE USAGE

These summaries and analyses will be conducted for the safety population unless specified otherwise.

11.1 Treatment Compliance

Treatment compliance for the double-blind study period (%) will be calculated and summarized by study drug and listed for the individual subject using the following formula:

Treatment compliance (%) = doses administered/ (number of planned visits between first and last dose, inclusive)*100. Visits which occur after the last dose will be excluded from the total dose planned per protocol.

11.2 Concomitant Medications

Information on concomitant medications (CMS) is collected throughout the study. The World Health Organization (WHO) Dictionary will be used to classify medications by preferred name, chemical ingredient names and WHO Level III Anatomical Therapeutic Chemical (ATC) classification of trade name. The dictionary version will be established and documented during the blinded data review period prior to lock of the data. Medication records will be characterized as part of the subjects' medical history for medications taken prior to the first dose of the study drug. Medication records will be characterized as CMS for all medications that have a start date following the first dose of the study drug.

CMS will be summarized for each treatment arm by ATC drug class and by the WHO drug preferred name. Subjects who report use of more than one medication or multiple uses of the same

medication will be counted once per medication code and once for all drugs taken within an ATC drug class.

CMS will also be summarized based on the number of subjects with changes to AD medication between the first and last dose of study treatment. The number of subjects will be presented along with the incidence of AD medications for each treatment arm by WHO drug preferred name.

The listing of medications will display entries from the CMS form, ordered within subject by the medication start date. The listing will display the recorded term from the CRF and, adjacent to that, the preferred name that appears in the tables.

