3.2 Number of Subjects and Sites for the Study

This trial will be conducted at approximately 30 global sites. The following sample sizes (mutation positive subjects) are specified for each drug with a 3:1 treatment to placebo randomization ratio:

1. Gantenerumab: 69 mutation positive subjects.
2. Solanezumab: 69 mutation positive subjects.

It is estimated that approximately 33% of all enrolled subjects will be mutation negative. The mutation negative subjects are not included in the above sample sizes. Recruitment will close for a study drug when the target number of mutation positive subjects for the study drug has been enrolled. Recruitment of mutation positive subjects with a Clinical Dementia Rating (CDR) > 0 may be closed if needed to ensure that no more than 50% of the required mutation positive subjects have a CDR > 0.

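### Section 11.2 counts as concomitant only medication started after the first dose, so drugs already in use at entry and continued on treatment drop out of the by-arm medication summaries

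*SAP*

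**What the plan says.** Section 11.2 of the SAP sorts medication records with two consecutive sentences. The first is: "Medication records will be characterized as part of the subjects' medical history for medications taken prior to the first dose of the study drug". The second is: "Medication records will be characterized as CMS for all medications that have a start date following the first dose of the study drug". No third category is given for a drug that spans the first dose.

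Two by-arm summaries are then built on CMS:

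- The general table: "CMS will be summarized for each treatment arm by ATC drug class and by the WHO drug preferred name".
- The AD-medication summary: "CMS will also be summarized based on the number of subjects with changes to AD medication between the first and last dose of study treatment". It is to be shown with the "incidence of AD medications for each treatment arm by WHO drug preferred name".

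There is also a subject-level listing: "The listing of medications will display entries from the CMS form, ordered within subject by the medication start date". No start-date cut is stated for it.

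Section 11 applies these summaries to the safety population. Section 3.3 allows entry at CDR 0.5 or 1, and section 3.2 lets recruitment be managed so that "no more than 50% of the required mutation positive subjects have a CDR > 0".

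**The concern.** A concomitant-medication table is normally read as showing what subjects were taking while on study treatment. Under the start-date rule it shows only what they began after the first dose. Long-term medication of any kind, taken unchanged from before entry to the end of follow-up, would not appear.

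The AD-medication summary is the more awkward case because the rule works against its stated aim. The summary is meant to capture changes between first and last dose. A change to an AD drug that the subject already took at entry is such a change, but the record concerned is not CMS.

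The trial admits symptomatic carriers, so some AD medication at entry is plausible. At stake is whether a reader of the study report can see, by arm, how many subjects entered on AD medication and what happened to it during treatment.

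**Working it through.** No arithmetic applies. The SAP gives no figure for medication use that could be reproduced, so the check is to pass each kind of record through the two sentences of section 11.2.

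1. **Started and stopped before the first dose.** Medical history, not CMS. This is the expected result.
2. **Started after the first dose.** CMS. This is also expected.
3. **Started before the first dose, continued unchanged.** It was taken before the first dose, so it is medical history. Its start date does not follow the first dose, so it is not CMS. It is absent from the ATC/preferred-name table and from the AD incidence.
4. **Started before, stopped during treatment.** Same classification as case 3. For an AD drug, the stop falls between first and last dose and is a change in the ordinary sense, but the record is outside CMS and the summary would not count it.
5. **Started before, dose changed within the same record.** The start date is unchanged, so the result is as in case 4.
6. **Started before, dose changed by closing the record and opening a new one.** The new record starts after the first dose and is CMS. Whether a dose change is counted therefore depends on how the site entered it.
7. **Started on the day of the first dose, with no time recorded.** Neither sentence clearly covers it.

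Cases 3 to 5 are the omission, case 6 is an inconsistency, and case 7 is a small gap of the same origin.

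The next step is to see whether another part of the SAP supplies what section 11.2 leaves out:

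- Section 10.2 tabulates medical history by body system and preferred term, or by disease-specific history. It is not by drug, so moving a medication record into medical history does not put it in a drug table.
- Section 10.1 covers demographics and the minimization factors. AD medication is not among the nine factors in Table 1 (section 3.4).
- Section 12.4.3.3 compares sex, APOE status, CDR-SB, age and education between placebo and DIAN-OBS subjects. Medication is not included.
- The gantenerumab and solanezumab appendices contain no rule on prior or ongoing medication.
- The listing in section 11.2 takes entries from the CMS form without a stated start-date cut. It may show the records in cases 3 to 5, but it gives no count by arm.

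So no planned by-arm summary shows AD medication in use at entry.

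**The case against.** Several points on the other side are fair.

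**The AD summary is announced as a summary of change, not of prevalence.** That is correct, and incidence can mean new use as well as frequency. The summary should not be faulted for failing to be a prevalence table. But case 4 stands on the narrower reading too: a stop during treatment is a change, and the CMS definition excludes the record.

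**A change presupposes a drug already taken, so the authors may have meant ongoing records to count.** This may well be the intention. In that case the two sentences and the summary disagree, and a programmer following the definition literally would still produce the incomplete table. It is a reason to correct the wording. The general ATC/preferred-name table has no such reading to rescue it.

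**The data are not lost.** This stands. The listing may carry the records, so an imbalance could perhaps be counted by hand. It narrows the gap without closing it.

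**No inference depends on these tables.** This stands. The primary model (section 12.1.3 and Appendix III) does not use CMS. Minimization also gives its heaviest weights to baseline CDR-SB (15) and EYO (10). If AD medication follows disease stage, that limits imbalance at entry without ruling it out.

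A reader might go further and infer that most AD-medication use predates the first dose, that the tables would therefore show only a small part of it, and that this hides a difference affecting the cognitive tests. The SAP does not support that. It gives no usage figures and says nothing about the effect of AD medication on the four tests. The 50% figure is a cap on carriers with CDR above 0, not an expected share. The appendices set follow-up at 48 months for the last subject and up to about 78 months for others, and section 12.2.3 plans an analysis of conversion from CDR 0, so many starts during the trial are equally plausible.

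**Conclusion.** Wrong as written, minor severity. On its plain text, section 11.2 omits medication started before and continued after the first dose from both by-arm CMS summaries. It also makes the AD-medication summary miss stops, and dose changes not entered as new records, among subjects already on an AD drug at entry.

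The size of the omission cannot be derived from the SAP: it depends on how many subjects entered on medication, and no figure is given. The effect is on descriptive safety-population tables only; the primary analysis is unaffected.

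The conclusion rests on two readings: that the CMS sentence is applied literally when the tables are programmed, and that both summaries use that definition, as their wording says.

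**What to change.** In section 11.2:

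- Define concomitant medication as any medication taken on or after the first dose, regardless of start date.
- Define prior-only medication as medication stopped before the first dose.
- State how a record starting on the day of the first dose without a time is classed.
- Tabulate AD medication in use at baseline by arm, separately from on-treatment starts, stops and dose changes by arm.

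The cost is a few sentences and a programming flag, with one extra block in the AD-medication table. No new data should be needed, provided the CMS form records a stop date or an ongoing indicator; the SAP does not describe the form, so this should be confirmed. No efficacy analysis changes.

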11.3 Substance Usage

Each subject's substance usage and frequency will be summarized for alcohol, caffeine, and tobacco. The distribution of subjects, including number and percentage of subjects, will be shown based on usage categories of never, current, and former, with substance usage captured per day, or per week. The univariate summary statistics, n , mean, standard derivation (SD), median, minimum, and maximum will be calculated for each usage category (never, current, and former) and use per day (when reported as either usage per day or per week).

12 EFFICACY ANALYSES

Statistical comparisons of treatment effects for all efficacy endpoints will be performed between each study drug arm and a variety of placebo arms such as the pooled control arm, the mutation positive placebo arm, or the direct placebo arm, respectively. No analyses comparing study drugs will be performed.

12.1 Analyses of the Primary Efficacy Endpoint

12.1.1 Visit Schedule for the DIAN-TU-001

The visit schedule for each study drug is described in its specific Protocol Appendix.

12.1.2 Calculation of the Analysis EYOs for the MDPM

EYO equals a subject's age at the clinical assessment minus this subject's estimated age at onset (AO). The estimated AO by mutation type was obtained from a published study [7] and is

presented in SAP [Appendix II](#) with more mutation variants and more age at onset data added in. If a subject's mutation type is not included in SAP Appendix II table, the estimated AO is set to the subjects' parental AO. If, in addition, the parental AO is unavailable, the estimated AO is set to the subjects' secondary degree relatives' AO.

For calculating EYO, the CRF visit date will be used for all tests in DIAN-MCE to ensure a constant value across all tests.

12.1.3 Primary Analysis of DIAN-MCE

The following analyses will be conducted for the mITT population and the eligible DIAN-OBS subjects.

A multivariate disease progression model (MDPM) with EYO time scale and a proportional treatment effect will be used to assess statistical differences in the rate of cognitive decline as measured by the four cognitive tests of DIAN-MCE simultaneously between each study drug arm, the mutation positive placebo arms (direct and concurrently randomized placebo subjects) and the eligible DIAN-OBS arm with dynamic borrowing in a single run (henceforth referred to as the 4-arm MDPM). The implementation of dynamic borrowing is presented in SAP [Section 12.1.4](#). The details of the MDPM are presented in SAP [Appendix III](#). Let the CPR denote the ratio of the rate of cognitive decline of one arm to the rate of cognitive decline of another arm. The MDPM will directly estimate three CPRs simultaneously. One is the ratio of the mutation positive placebo arm (post-baseline) to the eligible DIAN-OBS arm plus the baseline DIAN-TU-001 measurements (denoted as e^{θ_2}); the second is the gantenerumab active drug arm to the eligible DIAN-OBS arm (denoted as e^{θ_3}); and the third one is the solanezumab active drug arm to the eligible DIAN-OBS arm (denoted as e^{θ_4}). The treatment effect for each arm is reported compared to the mutation positive placebo arm. The treatment effect for gantenerumab is calculated using the posterior samples as $e^{\theta_3 - \theta_2}$ (or equivalently $\frac{e^{\theta_3}}{e^{\theta_2}}$), and for solanezumab as $e^{\theta_4 - \theta_2}$ (or equivalently $\frac{e^{\theta_4}}{e^{\theta_2}}$). The CPR that represents the treatment effect for each of the active drug arms ($\frac{e^{\theta_3}}{e^{\theta_2}}$ for gantenerumab and $\frac{e^{\theta_4}}{e^{\theta_2}}$ for solanezumab) will be relative to the mutation positive placebo.

The model behavior, the details for determining the threshold to control the type I error rate, and the estimated power are presented in SAP [Appendix VI](#).

The primary analysis for each study drug is testing the hypothesis that:

$$H_0: CPR \geq 1,$$

$$H_1: CPR < 1.$$

To test the null hypothesis that the active treatment (solanezumab or gantenerumab) does not slow down or stop the cognitive decline relative to the mutation positive placebos, the posterior probability of the alternative hypothesis is compared to a pre-specified threshold, 0.975 (specified in SAP [Section 12.1.5](#)). If it is greater than the threshold, then the null hypothesis will be rejected and the claim of superiority (cognitive progression slowing) will be made. The 95% credible interval (from the 2.5th to 97.5th percentiles) and posterior mean and median for each CPR will be presented. For the primary analysis, missing data are considered as missing at random.

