12.1.5 Thresholds for the Primary Analysis

The procedure for finding the appropriate thresholds for success on the primary analysis are as follows:

1. Simulations were conducted on each of the design scenarios defined in [Appendix VI](#) assuming that the null hypothesis is true for each treatment arm in the DIAN-TU-001 study.
2. The single threshold to the posterior probability is selected in order to maintain at most a one-sided 2.5% type I error rate in all null hypothesis scenarios.
3. If the threshold obtained in #2 is smaller than 0.975, then 0.975 is used. As a result, the simulated type I error rate will be less than 0.025 for all design scenarios.
4. The details are presented in Appendix VI. The threshold of probability of superiority determined by the simulation is 0.981. This threshold will be utilized in all the primary/secondary/sensitivity analyses for determination of statistical significance wherever the MDPM is used.

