This 97.5th percentile for each of these 13 scenarios (and combinations) is presented in [Table 16](#). The simulated type I error rate, using a probability of superiority threshold of 0.981, is reported in the last column.

Table 16: The 97.5th Percentile of the Posterior Probability of Superiority for the Null Hypothesis Scenarios. Using these as the threshold in that scenario would create a type I error rate of 2.5%.

	Simulation Scenario	97.5 th Percentile	Type I Error [contact]
A	Base	0.9678	0.013
B	Larger EYO	0.9713	0.015
	Smaller EYO	0.9723	0.016
C	2.5% Annual Drop-Out	0.9628	0.016
	10% Annual Drop-Out	0.9664	0.015
D	Correlation 0.25	0.9683	0.016
	Correlation 0.50	0.9669	0.012
	Correlation 0	0.9589	0.010
	Increased SD	0.9734	0.017
	Decreased SD	0.9653	0.010
E	Slower Decline	0.9801	0.023
	Faster Decline	0.9632	0.011
F	OBS N = 120	0.9599	0.009
Combined Nulls		0.9684	0.014

Post-Trial Permutation of Type I Error Rate

To justify that the model behaves similarly for the simulated data and for the actual patient data and to further verify the type I error rate, we will perform a null hypothesis permutation with the complete trial data. The details of this planned post-trial simulation are presented below. This post-trial simulation will be included in the CSR as supportive analyses for type I error control and a pure frequentist analysis of the Bayesian analysis. We permute the treatment assignment for randomized patients 10,000 times and calculate the frequency of these permutations that achieve the success threshold for the posterior probability and the frequency of permuted trials that achieve

the observed posterior probability for each arm as a permutation p -value. The permuted treatment assignments are all considered “null” scenarios.

- Using all the randomized subjects, a random permutation of the treatment code will be conducted. This will permute the treatment code of the 140 randomized patients. The primary analysis (4-arm MDPM; including the DIAN-OBS data) will then be applied to each of the 10,000 permuted datasets to estimate the CPR and posterior probability of superiority.
- The frequency of 10,000 permuted trials in which the posterior probability of superiority is greater than the pre-determined threshold will be reported and labeled as the “post-trial simulated type I error” of the trial. No pre-trial thresholds will be adjusted.

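### Section 12.1.3 tests the primary hypothesis against 0.975, while Section 12.1.5 and Appendix VI set the success threshold at 0.981

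*SAP*

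**What the plan says.** Section 12.1.3 defines the test of CPR < 1 for each drug. It states that "the posterior probability of the alternative hypothesis is compared to a pre-specified threshold, 0.975", attributing the number to Section 12.1.5. The decision follows: "If it is greater than the threshold, then the null hypothesis will be rejected and the claim of superiority (cognitive progression slowing) will be made".

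Section 12.1.5 sets out how the threshold is found. One value is to be "selected in order to maintain at most a one-sided 2.5% type I error rate in all null hypothesis scenarios". A floor then applies: "If the threshold obtained in #2 is smaller than 0.975, then 0.975 is used". The result is stated as "The threshold of probability of superiority determined by the simulation is 0.981", and its scope is explicit: "This threshold will be utilized in all the primary/secondary/sensitivity analyses for determination of statistical significance wherever the MDPM is used".

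Appendix VI selects the largest null 97.5th percentile. The type I error column of Table 16 is computed "using a probability of superiority threshold of 0.981".

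Appendix III also refers to a pre-determined threshold, but sends the reader to Appendix VII for it. Appendix VII is the gantenerumab appendix and contains no such threshold.

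**The concern.** Both numbers stand in current, operative text and govern the same decision, so a posterior probability of 0.978, for example, rejects the null under Section 12.1.3 and does not under Section 12.1.5. Each drug's confirmatory claim depends on this number, and other steps depend on it too:

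- For gantenerumab, CDR-SB and FAS are tested only if the primary analysis is significant (Appendix VII, Section 4.1).
- The pooled-drug analysis runs only when neither drug's primary analysis is significant (Section 12.4.3.1).
- The post-trial permutation type I error counts permuted datasets that exceed the pre-determined threshold (Appendix VI).

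If the conflict remains at unblinding, a result between the two values invites a dispute over which rule was pre-specified. The lower value also fails the SAP's own type I error requirement in one null scenario.

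**Working it through.** **Inputs.** Thresholds of 0.975 (Section 12.1.3) and 0.981 (Section 12.1.5, Appendix VI); the 0.975 floor (Section 12.1.5, step 3); the 13 null percentiles and type I errors in Table 16; 1,000 simulated trials per null scenario (Appendix VI).

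**1. Reproduce the stated threshold.** The largest of the 13 percentiles in Table 16 is 0.9801 (Slower Decline). The other 12 run from 0.9589 to 0.9734, and the combined-null value is 0.9684. Since 0.9801 > 0.975, the floor does not apply. Rounded up to three decimals, 0.9801 gives 0.981, which matches Section 12.1.5. At 0.981 the tabulated type I errors run from 0.009 to 0.023, so all 13 scenarios meet the 0.025 limit.

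**2. Direction of the error at 0.975.** In Slower Decline, 2.5% of the simulated null trials lie above 0.9801. A lower cut-off of 0.975 can only add rejections, so the simulated size there must be at least 0.025, and above it if any simulated value falls between the two. This step needs no distributional assumption.

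**3. Approximate size at 0.975 in Slower Decline.** The simulated posterior probabilities are not published, so this is an approximation. Assume the posterior z is normal with mean zero under the null:

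- SD of posterior z = z(0.9801) / z(0.975) = 2.056 / 1.960 = 1.049
- Size at 0.975 = 1 − Φ(1.960 / 1.049) = 1 − Φ(1.868) = 0.031
- Check at 0.981: 1 − Φ(2.075 / 1.049) = 0.024, against 0.023 in Table 16

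Two alternatives give a range:

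- Proportional tail: 0.025 × (0.025 / 0.0199) = 0.031
- Power law through the two tabulated points: exponent = ln(0.025/0.023) / ln(0.0199/0.0190) = 1.80; size = 0.025 × (0.025/0.0199)^1.80 = 0.038

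**4. Other scenarios, same normal approximation.**

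| Null scenario | Table 16 at 0.981 | Approx. at 0.981 | Approx. at 0.975 |
|---|---|---|---|
| Base | 0.013 | 0.014 | 0.019 |
| Increased SD | 0.017 | 0.018 | 0.024 |
| Slower Decline | 0.023 | 0.024 | 0.031 |

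The approximation fits least well for the 2.5% drop-out scenario (0.011 against 0.016 tabulated). That does not affect the conclusion, because all 12 other percentiles lie below 0.975.

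**5. Simulation error.** The Monte Carlo standard error at 0.025 is √(0.025 × 0.975 / 1000) = 0.005.

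**6. Power.** No threshold is stated for Table 15. Its CPR = 1 row agrees with the last column of Table 16 (for example 0.013 Base, 0.023 Slower Decline, 0.009 for OBS N = 120), so the stated power evidently rests on 0.981.

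**The case against.** The strongest reply is that the operative value can be worked out. Section 12.1.3 does not set 0.975 independently. It cites Section 12.1.5, and it also refers to Appendix VI for how the threshold is determined; both lead to 0.981. The 0.975 looks like the step 3 floor carried over. This is persuasive about intent and limits how far a result between the two values could really be argued either way. It does not remove the conflict. The SAP gives no precedence rule between these sections; its only such rule favours the drug-specific appendices, and neither sets a primary threshold.

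A second reply is that the type I consequence is small and uncertain. It concerns one of 13 scenarios, selected as the largest of 13 noisy estimates. With a standard error of 0.005, 0.031 is about 1.2 standard errors above 0.025. On the same normal scale, an approximate 95% range for the 0.9801 percentile is 0.970 to 0.987, which includes 0.975. This stands as a caution on size. However, the SAP's rule is applied to the simulated percentiles as tabulated, and by that rule 0.975 fails.

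A third reply concerns the credible interval. Section 12.1.3 reports a 95% interval, whose upper limit falls below 1 exactly when the posterior probability exceeds 0.975. It could therefore exclude 1 while the 0.981 test fails. The interval is descriptive, though, and Appendix III plans several levels (50%, 75%, 95% and 99%). It is not an error in itself.

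**Conclusion.** The point holds: the threshold in the section that defines the confirmatory test is wrong as written. The value 0.981 follows from the SAP's own selection rule and is the one behind the tabulated type I errors; 0.975 is only a floor that did not come into play.

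If 0.975 were applied, the Slower Decline null would exceed the SAP's 2.5% limit, at roughly 3.1% to 3.8% depending on the approximation, instead of the tabulated 2.3%. In the base null the normal approximation moves from about 1.4% to 1.9%, still within the limit. These sizes rest on assumed tail shapes and on 1,000 simulated trials per scenario, so they are indicative. The textual contradiction does not depend on them. It must be corrected because this number decides the primary claim for each drug.

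**What to change.** In Section 12.1.3, replace 0.975 with 0.981 and keep the reference to Section 12.1.5. In Appendix III, change the threshold reference from Appendix VII to Appendix VI. Both changes should be made before unblinding.

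Optionally, report a 96.2% equal-tailed interval (2 × 0.981 − 1 = 0.962, from the 1.9th to the 98.1th percentile) beside the 95% one, so that one reported interval agrees with the decision. This is a presentation choice and the correction does not depend on it.

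The cost is SAP wording only. No simulation needs rerunning, and since Table 15 evidently already rests on 0.981, the stated power is unchanged.
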